6.1.2 Non-Date Values

Quality of life

Missing values will be managed according to EORTC QLQ-C30 version 3.0 manual (see reference 1 for further information).

According to this manual, scores of scales involving missing items will be computed only if at least half of the items from the scale have been answered. The scale score will be calculated by using all the items that were completed (any items with missing values will be ignored). If more than half of the items are missing (or the missing item is a single question) than the scale score will be set to missing. This will be independently applied to the calculation of each scale score (global scale score, functional scale scores, symptom scale scores)

As the analysis of the quality of life data are descriptive, no additional efforts are made to impute missing items. Especially completely missing forms will not be imputed.

Transfusion independence

In the case of missing transfusion dates no imputation will be done. However, the patient is counted as transfusion independent, if a duration of 56 days or more is calculated for two consecutive transfusions with non-missing dates. For the remaining patients with missing or incomplete transfusion dates the patient is regarded as not transfusion independent, but the final decision about transfusion independence will be taken at the BDRM, using a conservative approach.

Other non-date values

Other non-date values will not be inputted in any of the analysis.

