6.5.2 Secondary Endpoints

6.5.2.1 Morphologic Complete Remission (CR) rate

6.5.2.2 *The CR rate is the proportion of patients who achieve a morphologic CR according to the IWG response criteria ([Appendix F](#)) in the absence of interceding therapies, including salvage treatments and HSCT, within the study period. Transfusion Independence (TI)*

Transfusion independence rate is defined as the proportion of patients who achieve eight weeks or longer with neither red blood cell (RBC) nor platelet (PLT) transfusions during the study period [[Fenaux, 2009](#); [Silverman, 2006](#)].

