- The number of surviving patients, the number of deaths and the number of patients with censored values will be displayed as well.
- Censoring patterns will be examined between treatment groups. Therefore the censored and not censored observations in the two treatment groups will be analyzed over time in a scatterplot.
- The effect of subsequent therapy on OS will be analyzed, including an analysis that compares OS in the treatment groups with censoring at the start date of the new interceding therapy, including those started during study treatment phase (concomitant therapy) and after stopping of study treatment as recorded in the new AML therapy eCRF page. Balance of such cases in the two treatment groups will be assessed to evaluate the appropriateness of this analysis method.
- Other sensitivity analyses will be performed to assess the robustness of OS results, if relevant. These will be decided prior to unblinding (e.g. at BDRM) based on real data.
- The primary OS analysis (stratified log-rank test) will be repeated for the PP set.
- Impact on OS of other baseline/demographic factors (including those considered for the subgroup analysis (section 5.3), plus possible others), will not be evaluated by means of Cox PH model(s) as initially planned due to the evident lack of the PH assumption for the treatment group factor.

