Transfusion independence rate is defined as the proportion of patients who achieve eight weeks or longer with no “relevant” transfusion during the study period.

The period of transfusion independence will be calculated for each patient as the duration (in days) from baseline (Cycle 1 Day 1) to the first “relevant” transfusion during the study period, and then between each subsequent “relevant” transfusion up to the last visit where this information was collected.

If at least one of the durations calculated is greater or equal to 56 days, the patient is regarded as transfusion independent within study period.

The proportion of patients who showed transfusion independence will be summarized by study treatment and transfusion dependence at baseline (patient received any kind of transfusion during the eight weeks prior to baseline).

In addition, the transfusion independence will be calculated separately for each of the relevant transfusions specified above. The proportion of patients who showed transfusion independence from RBC, PLT (whole blood transfusions are included in both categories for the calculations) will be also summarized by treatment.

The proportion of patients who are transfusion independent during study will be compared between the two treatment groups using the same methods as those used for the CR rate analysis including only treatment and stratification factor values documented at randomization. The analysis set will be the ITT set.

All transfusions will be listed.

Complete Remission without Minimal Residual Disease (CR_{MRD-}) rate

The CR_{MRD-} rate is the proportion of patients who achieve a CR with MRD negativity by multi-color flow cytometry, according to the IWG response criteria (Appendix F of the protocol) within the study period. Absence of interceding therapies is requested for considering the response in the analysis (for both CR and MRD negativity).

CR_{MRD-} rate will be analyzed on the ITT and EE-1 sets, using the same methods as those used for the CR rate analysis including only treatment and stratification factors (values stated at randomization). Patients for whom no assessment with multi-color flow cytometry is available at the planned timepoints will be analyzed as not having reached CR_{MRD-}. However patients from sites for which no assessment of MRD was possible due to logistic reasons will be excluded from the ITT/EE-1 sets.

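### For patients with a missing transfusion date, the transfusion-independence rule can credit a gap that the undated transfusion may have broken, and can also overlook genuine transfusion-free intervals

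*SAP*

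**What the plan says.** **Definition.** Protocol 6.5.2.2 counts patients who "achieve eight weeks or longer with neither red blood cell (RBC) nor platelet (PLT) transfusions during the study period". SAP 8.2 turns this into intervals: from Cycle 1 Day 1 to the first relevant transfusion, then between successive transfusions, "up to the last visit where this information was collected". The patient succeeds "If at least one of the durations calculated is greater or equal to 56 days".

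**Missing dates.** SAP 6.1.2 states: "In the case of missing transfusion dates no imputation will be done". It then counts the patient as independent "if a duration of 56 days or more is calculated for two consecutive transfusions with non-missing dates". Patients not credited in this way are treated as not independent, but "the final decision about transfusion independence will be taken at the BDRM, using a conservative approach" (BDRM: blind data review meeting).

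**Interceding therapy.** SAP 8.2 requires that no interceding AML therapy was given before a CR counts. For both CR without MRD and cytogenetic CR it says: "Absence of interceding therapies is requested for considering the response in the analysis". Neither the protocol nor the SAP sets such a condition for transfusion independence. SAP 8.1.2 and 8.2 do foresee new AML therapy begun during the treatment phase.

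**Place in the testing order.** SAP 5.4 ranks the endpoints CR, transfusion independence, CR without MRD, cytogenetic CR. SAP 5.5 splits the one-sided alpha for secondary endpoints into 0.002 at interim and 0.023 at final.

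**The concern.** A patient with a missing transfusion date is one whose transfusion-free time is uncertain. The rule for that patient looks only at the dates that exist, so an undated transfusion may sit inside the gap that earns the credit. The safeguards (failure by default, conservative decision at blind review) are written for the patients left over after the automatic credit. This sits badly with SAP 6.1.1, which resolves incomplete dates in the most conservative direction.

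The same rule is narrower than the main definition in one respect. It credits only gaps bounded by two dated transfusions, whereas SAP 8.2 also counts the opening and closing intervals. It can therefore fail patients whose independence is certain.

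Transfusion independence is a tested endpoint, and the tests of CR without MRD and cytogenetic CR depend on it. An error affects its own estimate and whether those two are formally tested. The missing interceding-therapy condition is a separate, smaller inconsistency.

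**Working it through.** **1. Credit across an undated transfusion.** Let the computed gap between two dated transfusions be G days, with one undated transfusion t days into it. The true intervals are t and G − t. The longest is at least 56 days for certain only if max(t, G − t) ≥ 56 for every possible t.

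- If t may be anywhere in the gap, the worst case is the midpoint, where the longer part is G/2 rounded up to a whole day.
- G = 110 gives 55 + 55, so no true 56-day interval. G = 111 gives at best 55 + 56, so one must exist.
- Computed gaps from 56 to 110 days can therefore be false successes. From 111 days they cannot, given a single undated transfusion.

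| True gaps (days) | Computed gap if the middle date is missing | Credited by 6.1.2? | Any true gap ≥ 56? |
|---|---|---|---|
| 21 + 21 | 42 | no | no |
| 28 + 28 | 56 | yes | no |
| 35 + 35 | 70 | yes | no |
| 42 + 42 | 84 | yes | no |
| 55 + 55 | 110 | yes | no |

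**2. The opposite error.** The two rules side by side:

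| Interval | Counted in SAP 8.2 | Credited automatically in SAP 6.1.2 when a date is missing |
|---|---|---|
| Cycle 1 Day 1 to first transfusion | yes | no |
| Between two dated transfusions | yes | yes |
| Last transfusion to last visit with this information | yes | no |

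Take a patient with one undated early transfusion and then 84 clear days (3 × 28) from the last dated transfusion to the last visit. SAP 8.2 would count this patient; SAP 6.1.2 starts from failure and leaves the outcome to the meeting.

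**3. Size.** The documents give no rate or power for transfusion independence, so there is no plan figure to reproduce. With 500 patients randomized 1:1 (Protocol 9.11), one patient is 1/250 = 0.4 percentage points of an arm.

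The nearest stated figures are for CR: 0.20 on placebo, difference 0.13 (SAP 5.5). I used the one-sided pooled-variance formula

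power = Φ{[(p1 − p0) − z·√(2p̄(1 − p̄)/n)] / √[(p0(1 − p0) + p1(1 − p1))/n]}.

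- n = 250, alpha 0.025: 0.911 (SAP Table 2: 0.91).
- n = 212 (85% of 250), alpha 0.002: 0.562 (SAP Table 3: 0.56).

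The formula reproduces the plan. For illustration only, **assume** that the true transfusion-independence rates equal those CR rates (0.20 and 0.33), with n = 250 and alpha 0.023. False credit f among truly non-independent patients changes a rate p to p + (1 − p)f; for example 0.20 + 0.80 × 0.05 = 0.24 and 0.33 + 0.67 × 0.05 = 0.3635.

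| Assumed false credit | Observed difference | Power |
|---|---|---|
| none | 0.130 | 0.905 |
| 5% in both arms | 0.1235 | 0.847 |
| 10% in both arms | 0.117 | 0.781 |
| 5% placebo only | 0.090 | 0.593 |
| 5% pracinostat only | 0.1635 | 0.982 |

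With no true difference (0.20 in both arms), false credit of 2.5% or 5% in the pracinostat arm alone would raise the rejection rate from 0.023 to 0.074 or 0.180. Nothing in the documents indicates which of these rows applies.

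**4. Interceding therapy.** Three of the four secondary endpoints carry the condition; transfusion independence does not. How far this reaches depends on data collection:

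- Protocol 4.7.3 requires study treatment to stop before another anticancer agent is given.
- The schedule of assessments ends concomitant-medication recording 30 days after the last study drug, or at new AML therapy if earlier. Protocol 4.7 runs it to the End of Treatment visit.
- Long-term follow-up contacts (Protocol 5.2) do not list transfusions.
- With the End of Treatment visit at 30 ± 2 days, a 56-day interval must include 56 − 32 = 24 to 56 − 28 = 28 days before the last dose. At most about 28 to 32 of its days fall after treatment stops.

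What remains is mainly AML therapy given during the treatment phase, plus that tail of roughly 30 days.

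**The case against.** The strongest reply is that consecutive means truly consecutive: two transfusions with an undated one between them do not qualify. Transfusions are reviewed visit by visit (Protocol 5.1.5, 5.1.8 and 5.1.10), and the transfusion listing in SAP 14 is sorted by visit and then date, so an undated record can often be put in order. This reading is possible, but the text does not secure it. A record cannot always be ordered, and the SAP does not say to order by visit.

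Three stronger readings are tempting and are not supported.

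- **That the rule simply inflates success.** It does not: step 2 shows it can also fail patients who qualify under SAP 8.2.
- **That it favours pracinostat.** The documents give no rate of missing dates and no reason for the arms to differ. Dates are specifically to be collected (Protocol 4.7 and 6.1.2), and equal false credit mainly dilutes the difference.
- **That patients are credited for eight weeks on post-discontinuation salvage therapy.** A full 56 days of that kind does not fit the scheduled collection.

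It is also fair to say that the documents define the endpoint over the study period, not on study treatment. Asking for the same interceding-therapy condition as for the response endpoints seeks consistency; it does not correct a contradiction. Finally, the endpoint is tested only after OS and CR succeed, and SAP 8.1.2 makes the secondary analyses exploratory if the trial stops at interim. The reported rates would still carry any error.

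**Conclusion.** The point holds as a defect in the missing-date rule, of minor weight. As written, SAP 6.1.2 permits credit for a computed gap of 56 to 110 days that one undated transfusion may have broken, and places that credit ahead of the conservative safeguards. It also leaves out two interval types that the main definition counts. The range of 56 to 110 days assumes a single undated transfusion that cannot be placed more precisely.

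The effect is 0.4 points of an arm's rate per misclassified patient. The number of such patients and the direction between arms are unknown, and the power figures above rest on borrowed CR rates and assumed error rates. The documents show that the rule can misclassify, not that it will do so to a material extent.

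The absence of an interceding-therapy condition is a genuine inconsistency with the other three secondary endpoints, but narrow in reach.

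**What to change.** **Missing or partial transfusion dates (SAP 6.1.2).** Credit independence only if at least one interval of 56 days or more, of any type counted in SAP 8.2, survives every possible placement of the undated transfusion. Bound the placement by the partial date or by the visit interval in which the transfusion was reported. Otherwise count the patient as not independent. For example, in an 84-day gap:

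- bounded to days 56 to 84, the worst case leaves 56 clear days, so credit;
- bounded to days 28 to 56, placement at day 42 leaves 42 + 42, so no credit from this gap.

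Apply the same rule to the separate red-cell and platelet summaries, and keep the present rule as a sensitivity analysis.

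**Interceding therapy (SAP 8.2).** End the transfusion-free interval at the first interceding therapy as defined in SAP 7.8 and 8, and say what the study period means for this endpoint.

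**Cost.** A few sentences and a small derivation change, using data already collected. The rates may become slightly lower, though counting the opening and closing intervals may offset part of that. SAP 11 records that its latest version followed unblinding of the interim results, so the amendment should state when it was made, and both versions of the analysis should be reported.

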6.2 VISIT WINDOWS

Values will be presented for all scheduled study visits according to the nominal visit obtained from the CRF. If an unscheduled visit falls in a visit window with an existing nominal visit assessment, the nominal assessment will be used for summary presentation. All unscheduled assessments are to be assigned to the latest initiated cycle based on the date of the assessment.

All visits will be included in the data listings.

6.3 STUDY PERIODS

A patient is considered to have performed a cycle if during that cycle at least one dose of either AZA or PRAN/Placebo was administered to the patient, according to the Drug administration forms (Cycle x Day 1 drug administration /Pracinostat/placebo (for PRAN/PLAC) and drug administration – azacitidine forms (for azacitidine)).

A patient is to be considered entered in the long-term follow-up if:

1. Has at least one long-term follow-up visit filled (including the visit of End of Long-term Follow-up),

OR

2. Was discontinued from active treatment phase for reasons other than death, lost to follow-up, withdrawal by subject (*).

(*) Withdrawal by subject will be considered a criterion for not entering long-term follow-up only when it is reported in the eCRF as the reason for stopping both treatment and long-term follow-up phases and the dates of stop of treatment and long-term follow-up are equal.

6.4 DATA DERIVATIONS AND DEFINITIONS

When reporting durations in months, divide the number of days by 30.4375; to report in weeks divide the number of days by 7; to report in years divide the number of days by 365.25. These algorithms for durations / time to event return decimal numbers, and ignore the actual numbers of days in the months or years between start date and stop date. The "year" used in these algorithms is 365.25 days long, and the "month" is one twelfth of that year.

Durations and time to events will be analyzed in days.

Baseline is defined as measurement obtained at the most recent assessment prior to the date of the first study treatment dose. Change from baseline will be calculated as the difference between the respective visit value and the baseline value.

Age will be calculated from the date of birth to Screening date.

For the calculation of exposure to study drug the Body Surface Area (BSA) is needed. If the baseline BSA is not documented, the next available documented BSA within the study period will be used for the calculation of the exposure.

The following will define pre-treatment use versus concomitant medication use:

- Prior use ending before receiving the first administration of study drug will be defined as "pre-treatment medications".
- Medications that started prior to the first administration of study drug, and continued pass through the first administered dose date as well as medication started after the first administered dose date will be defined as concomitant medications.

In a similar way, prior and concomitant procedures will be defined as:

- Prior procedures ending before receiving the first administration of study drug will be defined as "prior procedures".

- Procedures that started prior to the first administration of study drug, and continued pass through the first administered dose date as well as procedures started after the first administered dose date will be defined as concomitant procedures.

TEAEs will be considered as any event occurring, or a pre-existing event worsening, on or after receiving the first intake of pracinostat /placebo, and up to 30 days after receiving the last administration of study drug (date reported in the field Date of Last Pracinostat/Placebo Administration in the Subject Disposition page of the CRF will be used as the reference point).

Each TEAE is collected in the eCRF by recording one initial record and one record for each change in seriousness and/or severity within the same occurrence of the event. A summary record will be derived aimed at being used for the production of the summary tables, while individual records will only be listed.

The summary record will pick-up among the collected records relevant to the same event (it is allowed to collect one field from one record and another field from another record) the maximum seriousness and the maximum severity. Actions taken will be picked up from all the records in order to keep all the actions taken with the event. The outcome will be picked up from the last record in time-sequential order. The relationship will be reconciled during data cleaning, so it will be the same in all of the records related to the same event at time of analysis.

As MRD (positive/negative) will be obtained together with the other data related to MRD analyses from the external lab, CR_{MRD} will be derived in the CDISC datasets from CR and MRD results.

Adverse events of special interest (as described in the study protocol) will be retrieved according to the following rules reported in the table:

AESI	MedDRA SMQ (v.20.0)	MedDRA PT (v. 20.0)	Comments
QTc prolongation	Torsade de Pontes/QT prolongation (SMQ) - NARROW	n/a	
Supraventricular arrhythmias	Supraventricular tachyarrhythmias (SMQ) - NARROW	n/a	
Sepsis, septic shock, grade ≥ 3 lung infection (pneumonia), any infection leading to death	Toxic-septic shock conditions (SMQ) - NARROW	1.Any PT that includes the word sepsis 2.Exact match to the PT pneumonia or lung infection	Pneumonia only if grade ≥ 3

Grade ≥ 3 anemia, neutropenia, febrile neutropenia and thrombocytopenia	n/a	
1.Any PT that includes the word anaemia.
 
2.Exact match to any of the following PTs:
 
Haemoglobin decreased Band neutrophil count decreased Band neutrophil percentage decreased Febrile neutropenia Granulocyte count decreased Granulocytopenia Neutropenia Neutropenic infection Neutropenic sepsis Neutropenic colitis Neutrophil count decreased Neutrophil percentage decreased Platelet count decreased Platelet production decreased Thrombocytopenia Febrile bone marrow aplasia
	All listed PTs only if grade ≥ 3
Grade ≥ 3 haemorrhage	n/a	Any PT that includes the word haemorrhage or haematoma or bleeding	All listed PTs only if grade ≥ 3

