- Biomarker analysis (if consent obtained by patient): Peripheral blood samples and/or aspirate bone marrow samples will be collected and stored for potential molecular studies (Section 6.4)

5.1.3 Cycle 1 on Day 1

After confirmation of eligibility, the patient will be randomized to one of the two treatment groups using the IWRS. The following activities are to be performed **before study treatment administration**:

- Assess transfusions of red blood cells or platelets performed during the previous 8 weeks (Section 6.1.2).
- Perform a limited physical examination
- Measure blood pressure and pulse rate –**pre-dose** (sitting or in semi-supine position), body temperature, and weight
- 12-lead ECG measurement in triplicate - **pre-dose**
- Collect concomitant medications and any new medical conditions since the screening visit
- Assess ECOG performance status
- Administer the Quality of Life questionnaire
- Urine pregnancy test for women of childbearing potential – **pre-dose**
- Re-check of all eligibility criteria
- Assessment of adverse events
- Randomization via IWRS: The IWRS will provide the investigator with the kit number stored in the site stock to be dispensed to the patient.
- Treatment administration: The study treatment administration schedule is the following:
 - Pracinostat/placebo administration (see Section 4.2): according to the indication reported on the study kit internal panel, the patient will receive 1 capsule of study drug or matching placebo (week 1, day 1). Patient must begin study treatment within 24 hours after randomization.
 - Azacitidine administration: according to indication reported in Section 4.3.1.2 azacitidine is administered to patient.

Pracinostat/Placebo oral administration is to be taken before administration of azacitidine.

The date and the precise time (hh:mm) of the study drug and Azacitidine administration as well as other information related to the quantity and origin of the Azacitidine vials must be recorded in the source records as well as on the relevant eCRF page for each medication given. The relevant peel-off labels from the study kit and from the Azacitidine commercial packs used for the treatment at this visit will be attached to the drug accountability log (pharmacist or designated responsible).

Activities to be performed **after study drug administration (for all patients EXCEPT those participating in the AZA/pracinostat PK sub-study**. See Section 6.3):

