9.7.5 Quality of Life

Quality of life will be evaluated using the EORTC QLQ-C30 questionnaire.

Summary tables of absolute value and change from baseline at the different timepoints will be produced. Baseline will be the last value available before the first study drug administration on Day 1 of Cycle 1. The global health status and some of the functional scales or symptom scales, which will be defined in the SAP, will be analyzed.

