 - (3) on Day 15 of Cycle 1 only

(4) at any time during EoT visit

Body weight will be measured:

- (1) at screening
- (2) on Day 1 all Cycles
- (3) at any time during EoT visit

H Complete physical examination will be performed at Screening. This evaluation will include an examination of general appearance, head, eyes, ears, nose, throat, skin, neck, lungs, cardiovascular, breast, lymph nodes, abdomen, musculoskeletal and neurological.

Limited physical examination, covering general appearance, cardiovascular, lungs and abdomen body systems, will be performed at Day 1 of each cycle to assess any changes that may have occurred since the last examination.

I ECOG performance status will be evaluated at screening and on Day 1 of each Cycle and EoT visit

J Information on transfusion of RBC or platelets (including date and type of transfusion) will be collected: at Day 1 of Cycle 1 (Section 5.1.2 of study protocol) and between Day 21 and Day 26 of Cycle 2 and all subsequent even cycles.

K Quality of Life Questionnaire to be administered on Day 1 Cycle 1 and on each Day 1 of odd Cycles and EoT visit.

L Triplicate 12-lead ECGs will be recorded (after the patient has been in sitting or in semi-supine position for at least 5 minutes):

- (1) at screening
- (2) on Day 1 of Cycle 1 (predose; at 90 minutes \pm 30minutes and 6 hours \pm 30minutes post pracinostat/placebo administration), on Day 2 of Cycle 1 (at 24 hours \pm 1hours post pracinostat/placebo administration), on Day 3 of Cycle 1 (at 48 hours \pm 1hours post pracinostat/placebo administration), on Day 15 of Cycle 1 (at 90 minutes \pm 30minutes post pracinostat/placebo administration),
- (3) on Day 1 of Cycle 2 (predose; at 90 minutes \pm 30minutes post pracinostat/placebo administration),
- (4) during the visit from Day 21 to Day 26 of Cycle 2 (any time)

Single 12-lead ECGs will be collected 90 \pm 30 minutes post pracinostat/placebo administration on Day 1 of each subsequent Odd cycle (i.e., Cycles 3, 5, 7, 9).

M Laboratory tests will be performed at a central laboratory. Samples for CBC, serum chemistry and coagulation are to be collected:

- (1) at screening within 8 days prior to Day1 of Cycle 1
- (2) at Day 15 of Cycle 1 only
- (3) at Day 1 of Cycle 2 only
- (4) between Day 21 and Day 26 starting from Cycle 2 and for all the subsequent Cycles
- (5) at any time during EoT visit

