8.4 QUALITY OF LIFE

Quality of life will be evaluated using the EORTC QLQ-C30 questionnaire.

The following scores will be analyzed by treatment group presenting absolute score value and change from baseline for the different visits where the questionnaire was to be filled in:

- Global Health Status / QoL (questions 29, 30)
- Functional Scale “Physical Functioning” (questions 1 to 5)
- Functional Scale “Role Functioning” (questions 6,7)
- Symptom Scale / Item “Fatigue” (questions 10, 12, 18)
- Symptom Scale / Item “Nausea and Vomiting” (questions 14, 15)
- Symptom Scale / Item “Appetite Loss” (question 13)

All other functional and symptom scale scores will be computed and listed. These are

- Functional Scale “Cognitive Functioning” (questions 20, 25)
- Functional Scale “Emotional Functioning” (questions 21 to 24)
- Functional Scale “Social Functioning” (questions 26, 27)
- Symptom Scale / Item “Pain” (questions 9, 19)
- Symptom Scale / Item “Dyspnoea” (question 8)
- Symptom Scale / Item “Insomnia” (question 11)
- Symptom Scale / Item “Constipation” (question 16)
- Symptom Scale / Item “Diarrhoea” (question 17)
- Symptom Scale / Item “Financial Difficulties” (question 28).

The analysis set will be the ITT set.

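### SAP 6.4 sets baseline before the date of first dose, which read literally excludes the Cycle 1 Day 1 pre-dose QLQ-C30 for patients dosed that day and contradicts protocol 9.5 and 9.7.5

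*SAP*

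**What the plan says.** The general derivation rule in SAP 6.4 reads: "Baseline is defined as measurement obtained at the most recent assessment prior to the date of the first study treatment dose". The next sentence adds: "Change from baseline will be calculated as the difference between the respective visit value and the baseline value".

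SAP 8.4 analyses six QLQ-C30 scores by treatment group (global health status, physical functioning, role functioning, fatigue, nausea and vomiting, appetite loss), "presenting absolute score value and change from baseline for the different visits". It does not say what baseline means for these scores.

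On timing, note K of the SAP 3.2 schedule says: "Quality of Life Questionnaire to be administered on Day 1 Cycle 1 and on each Day 1 of odd Cycles and EoT visit". In protocol 5.1.3 the item "Administer the Quality of Life questionnaire" stands in the list of activities to be done before treatment on Cycle 1 Day 1.

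Protocol 9.7.5 has its own rule for quality of life: "Baseline will be the last value available before the first study drug administration on Day 1 of Cycle 1".

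**The concern.** A rule tied to the date of first dose and a rule tied to the first dose itself give different answers for anything measured on the dosing day before the dose. For most variables this matters little, because there is a screening value to fall back on or a separate baseline definition. Quality of life has neither within the SAP. Its only pre-treatment measurement is planned for the day on which dosing is planned to start.

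At stake is whether the planned change-from-baseline summaries for quality of life contain the patients they should. A programmer working from the SAP alone would set the baseline to missing for patients dosed on the day of the form. The risk is practical, because the questionnaire reproduced in protocol Appendix K asks for the date of completion and not the time, so a comparison of dates is the natural way to program the derivation.

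**Working it through.** The plan gives no figure to reproduce and no arithmetic applies. The check is a comparison of definitions with the schedule.

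**Step 1. Baseline definitions side by side.**

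| Place | Cut-off | Same-day pre-dose value accepted? |
|---|---|---|
| SAP 6.4, general | Date of first dose | No, read literally |
| SAP 8.4, quality of life | None given | Defaults to 6.4 |
| SAP 9.4, 9.5, 9.6 (laboratory, vital signs, ECG) | First administration | Yes |
| SAP 8.2, transfusion independence | Cycle 1 Day 1 itself | Yes |
| Protocol 9.5, general | First dose | Yes |
| Protocol 9.7.5, quality of life | First study drug administration on Cycle 1 Day 1 | Yes |

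SAP 6.4 is the only definition that turns on the date.

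**Step 2. Is there an earlier form?** The screening procedures in protocol 5.1.2 include no questionnaire, and the screening cells for quality of life are empty in protocol Appendix A and in SAP 3.2. The Cycle 1 Day 1 form is the only one scheduled before treatment.

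**Step 3. Could imputation supply a baseline?** No. SAP 6.1.2 does not impute forms that are missing altogether.

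**Step 4. Apply each rule.** Let F be the date of the form and D the date of first dose. SAP 6.4 requires F < D.

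- *F = D.* The condition fails and no earlier form exists. The baseline is missing, so visit value minus baseline is missing at every visit and for all six scores.
- *D is the day after F.* This is possible because protocol 5.1.3 says: "Patient must begin study treatment within 24 hours after randomization". The condition holds and the baseline exists.
- *Protocol 9.7.5.* The form only has to precede the dose. Both kinds of patient have a baseline.

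**Step 5. Was the narrower rule declared?** SAP section 11 lists five changes that are not reflected in the protocol. None concerns the baseline definition.

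**Step 6. How many patients?** The documents do not say how many were dosed on the date of the form. In principle the number runs from none to all patients with a Day 1 form. Protocol 5.1.3 places the questionnaire, randomization and the first capsule in one visit, so I assume that same-day dosing is the usual case.

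**The case against.** A reader might infer that change from baseline in quality of life cannot be computed at all, or that the tables must come out empty. The documents do not support that. Protocol 9.7.5 gives a workable definition specific to quality of life, and the SAP nowhere says that it departs from it. An analyst who follows the protocol gets results. Patients first dosed on the next calendar date keep a baseline even under the literal SAP rule.

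It can also be argued that the SAP, read as a whole, does not mean to exclude pre-dose Day 1 values. SAP 8.2 equates baseline with Cycle 1 Day 1 for transfusion independence, SAP 7.2 reports baseline ECOG at randomization and at Cycle 1 Day 1, and SAP 9.4 to 9.6 use the first administration. SAP section 11 mentions a dry run before the interim analysis, where a nearly empty change table would probably have been noticed. That last point is inference, since the documents show no quality-of-life output.

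These arguments limit the likely consequence and suggest that the wording was unintended. They do not remove the contradiction. The SAP states a rule, that rule gives the wrong result for this variable, and the definition that would rescue it stands in another document to which SAP 8.4 does not refer.

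**Conclusion.** The point holds as an undeclared inconsistency in the SAP. It rests on reading the 6.4 wording as a comparison of dates and on 6.4 governing SAP 8.4 by default.

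The effect is confined to the quality-of-life change summaries. Absolute scores by visit do not use a baseline. Laboratory, vital-sign and ECG summaries have their own definitions and are not exposed.

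Severity is low. Quality of life is listed as exploratory in SAP 2.3.3, is described as descriptive in SAP 6.1.2 and lies outside the fixed testing sequence of SAP 5.4. Nobody should read this as a threat to the overall survival comparison, the significance levels or the power, because none of them uses this baseline.

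**What to change.** Reword the SAP 6.4 sentence along these lines: *baseline is the last non-missing value obtained before the first administration of study treatment, including pre-dose assessments on Cycle 1 Day 1*. Naming the Day 1 assessments tells the programmer how to treat a form that carries a date but no time.

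Alternatively, leave 6.4 alone and restate the protocol 9.7.5 definition in SAP 8.4. The first option is better because it also brings the general rule into line with protocol 9.5 and SAP 9.4 to 9.6.

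The cost is one sentence, plus a check that the derivation program accepts same-day pre-dose forms. No test, endpoint or data collection changes.
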